## **2.6.4 Other safety data**

### **2.6.4.1 ECG and cardiac imaging data**

Not applicable

### **2.6.4.2 Vital signs**

Vital signs were recorded at every study visit, and included

- Radial pulse rate (bpm)
- Systolic blood pressure (mmHg)
- Diastolic blood pressure (mmHg)
- Weight (kg)
- BMI (kg/m^2)

Abnormalities according notable criteria (see Appendix 2 of the study protocol) were identified. The proportions of patients with clinically notable abnormalities according to the notable criteria were summarized. Descriptive statistics of absolute values as well as change from baseline of all vital signs variables were presented by visit and treatment group. Only assessments obtained up to 28 days after the discontinuation of study medication was considered “on-treatment” and analyzed with relationship to immunosuppressive therapy.

## **2.7 Pharmacokinetic endpoints**

Everolimus C0-h whole blood levels were summarized by visit using descriptive statistics. Tacrolimus C0-h whole blood levels were summarized by visit and treatment group using descriptive statistics.

Trough levels of everolimus and tacrolimus, respectively, were summarized descriptively by visit. The number of patients with deviations from the therapeutic window (see Section 4 of the protocol) were counted and tabulated separately by visit and in total.

## **2.8 PD and PK/PD analyses**

Not applicable

## **2.9 Patient-reported outcomes**

Not applicable

## **2.10 Biomarkers**

HCV viral load (HCV-ribonucleic acid (RNA) levels overall and by genotype) was summarized descriptively by visit and treatment group.

## 2.11 Other Exploratory analyses

Not applicable

## 2.12 Interim analysis

An external and independent Data Safety Monitoring Board (DSMB) was instituted before study start. The DSMB reviewed safety-related issues in a meeting and was entitled to make recommendations for changes in study conduct.

## 3 Sample size calculation

The trial tests the null hypothesis that there was no difference in renal function, estimated by eGFR according to the MDRD-4 formula, at 12 months after randomization between the everolimus-based tacrolimus-minimization regimen and the tacrolimus-based control regimen versus the alternative hypothesis that the difference is 7.0 ml/min/1.73m^2. A sample size of 105 in each group will have 80% power to detect a difference in means of 7.0 ml/min/1.73m^2 assuming that the common standard deviation was 18.0 ml/min/1.73m^2 with a 5% two-sided significance level. (One will decide in favor of H1 when the difference in means would be 5.1 ml/min/1.73m^2 or greater in favor of the everolimus-based group.) To adjust the sample size for a common drop-out rate (DOR) of 20% (using the formula  $N_{adj}=N/(1-DOR)^2$ ), 165 patients need to be randomized per group. Sample sizes were estimated using NQuery (Version 6.1) procedure “Two-group t-test for equal means (equal n’s)”.

Power for the analysis of secondary variables was not investigated.

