## 5 Population

The study population will consist of *de novo* liver transplant recipients who will be enrolled prior to LTx and randomized 7 to 21 days post LTx in a 1:1 ratio to either everolimus (EVR)

in co-exposure with tacrolimus (TAC) at a reduced dose (< 5ng/ml) or TAC (6-10 ng/ml). 330 evaluable patients (165 in each treatment group) will be recruited.

The study will be conducted in 15 transplant centers in Germany.

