### **10.4.2 Statistical hypothesis, model, and method of analysis**

The trial tests the null hypothesis that the treatment difference (investigational minus control) in mean eGFR at Month 12 after baseline is zero versus the alternative hypothesis that the treatment difference is different from zero.

The hypotheses will be tested with an analysis of covariance (ANCOVA) with treatment , center, HCV-Class (positive, negative) and MELD ( $\leq 30$  vs  $> 30$ ) as factors, and eGFR at Visit 1 (Baseline) as covariate. Raw as well as adjusted means (= LS-means, LS: least square means) will be presented for the treatment contrast together with a two-sided *p* value and the appropriate confidence interval, respectively. The significance level will be 5% (two-sided). There are no multiplicity issues to be addressed since only the hypothesis of superior efficacy of the investigational vs. the control regimen will be tested confirmatory.

The Full Analysis Set will be used for the primary analysis. If patients of the FAS are switched from the reference to the investigational group during the study, they will be analyzed in their randomized group. If appropriate, a subgroup analysis will be performed comparing patients of the reference group with and without switch to the investigational group including a further analysis comparing the subgroups to the randomized investigational group. If treatment will be modified in the investigational group, they will be analyzed as randomized.

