## **10.7 Sample size calculation**

The trial tests the null hypothesis that there is no difference in renal function, estimated by cGFR according to the MDRD-4 formula, at 12 months after randomization between the everolimus-based tacrolimus-minimization regimen and the tacrolimus-based control regimen versus the alternative hypothesis that the difference is 7.0 ml/min/1.73m^2. A sample size of 105 in each group will have 80% power to detect a difference in means of 7.0 ml/min/1.73m^2 assuming that the common standard deviation is 18.0 ml/min/1.73m^2 with a 5% two-sided significance level. (One will decide in favor of H1 when the difference in means would be 5.1 ml/min/1.73m^2 or greater in favor of the everolimus-based group.) To adjust the sample size for a common drop-out rate (DOR) of 20% (using the formula  $N_{adj}=N/(1-DOR)^2$ ), 165 patients need to be randomized per group. Sample sizes were estimated using NQuery (Version 6.1) procedure “Two-group *t*-test for equal means (equal n’s)”.

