### **2.3.4 Statistical hypothesis, model, and method of analysis**

The trial tests the null hypothesis that the treatment difference (investigational minus control) in mean eGFR at Month 12 after baseline is zero versus the alternative hypothesis that the treatment difference was different from zero.

The hypotheses was tested with an analysis of covariance (ANCOVA) with treatment , center, HCV-Class (positive, negative) and lab MELD ( $\leq 30$  vs  $> 30$ ) as factors, and eGFR at Visit 2 (Baseline) as covariate. Raw as well as adjusted means (= LS-means, LS: least square means) were presented for the treatment contrast together with a two-sided p value and the appropriate confidence interval, respectively. The significance level was 5% (two-sided). There are no multiplicity issues to be addressed since only the hypothesis of superior efficacy of the investigational vs. the control regimen was tested confirmatorily.

The Full Analysis Set was used for the primary analysis. Patients will be analyzed in their randomized group.

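### The stated decision threshold of 5.1 mL/min/1.73m² does not follow from the plan's own inputs, which give 4.9, and it does not match the specified two-sided 5% ANCOVA

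*SAP*

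**What the plan says.** Protocol 10.7 and SAP 1.1 and 3 carry essentially the same sample size paragraph. Its inputs are a true difference of 7.0 mL/min/1.73m², a common SD of 18.0 and 1:1 allocation, sized with the nQuery two-group t-test "with a 5% two-sided significance level". The stated result is "A sample size of 105 in each group will have 80% power". A 20% drop-out rate, applied as N/(1−DOR)², then gives 165 randomised per group.

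Between the power statement and the drop-out adjustment there is a parenthesis: "One will decide in favor of H1 when the difference in means would be 5.1" mL/min/1.73m² or more in favour of the everolimus group. Protocol 10.7 has the same figure ("when the difference in means would be 5.1").

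The analysis sections define the confirmatory decision differently. Protocol 10.4.2 and SAP 2.3.4 specify an ANCOVA with treatment, center, HCV class and MELD class as factors and baseline eGFR as covariate. Protocol 10.4.2 reads "The significance level will be 5% (two-sided", and SAP 2.3.4 has the same sentence in the past tense. Neither section mentions a minimum observed difference. Both say that this is the only hypothesis tested confirmatorily.

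**The concern.** The parenthesis is worded as a rule for accepting H1, and nothing marks it as illustrative. It should therefore equal the smallest difference that the planning t-test would call significant. It looked too large for an SD of 18 with 105 per group.

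If it is wrong, the plan has two decision statements for its only confirmatory hypothesis. An observed difference between the true critical value and 5.1 would be significant under the specified test but would fail the written rule, and no section says which prevails. The primary analysis uses the FAS with LOCF (SAP 2.3.4, 2.3.5 and 5.2), so dropouts with an eGFR value remain in it and the number analysed can exceed 105 per group. A cut-off fixed at the planning stage then moves further from the 5% test.

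**Working it through.** **Inputs** (Protocol 10.7; SAP 1.1 and 3): difference 7.0, SD 18.0, n = 105 per group, two-sided α = 0.05, two-group t-test with equal n, drop-out 20%.

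**1. Reproduce the plan's other figures.**
- Power at n = 105 for a difference of 7.0 (noncentral t, 208 df) is 80.1%. At n = 104 it is 79.7%. So 105 is the smallest n reaching 80%.
- Inflation: 105/(1 − 0.20)² = 105/0.64 = 164.06, which rounds up to 165.

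Both agree with the plan.

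**2. Recompute the threshold.**
- Standard error = 18 × √(2/105) = 2.484.
- Critical value t(0.975; 208) = 1.971.
- Smallest significant difference = 1.971 × 2.484 = **4.90**, against 5.1 stated.
- At an observed 5.1, t = 5.1/2.484 = 2.053 and the two-sided p value is 0.041.

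**3. Look for a variant that gives 5.1.**
- Normal quantile: 1.960 × 2.484 = 4.87.
- One-sided 5%: 1.652 × 2.484 = 4.10.
- SD anywhere from 17.95 to 18.05 (rounding of 18.0): 4.88 to 4.91.
- 132 per group (165 × 0.8): 4.36. 165 per group: 3.90.
- SD needed at n = 105: 5.1/(1.971 × √(2/105)) = 18.74 (18.6 to 18.9 if 5.1 is itself rounded).
- n needed at SD 18: about 97 per group, which gives 5.10.

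No standard variant of the stated inputs gives 5.1, and the documents contain neither an SD near 18.7 nor 97 per group.

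**4. Size of the discrepancy if 5.1 were applied literally.** Here alpha is the two-sided p value at an observed 5.1. Power with the 5.1 cut-off is Φ((7.0 − 5.1)/SE). Power of the 5% test is from the noncentral t. SD is 18 without covariate adjustment.

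| n per group | SE | 5% threshold | Alpha at 5.1 | Power at 7.0, 5.1 cut-off | Power at 7.0, 5% test |
|---|---|---|---|---|---|
| 105 | 2.484 | 4.90 | 4.1% | 77.8% | 80.1% |
| 132 | 2.216 | 4.36 | 2.2% | 80.4% | 88.2% |
| 165 | 1.982 | 3.90 | 1.05% | 83.1% | 94.1% |

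The 165 row is an upper limit: every planned patient analysed.

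**5. The ANCOVA threshold.** This depends on a residual SD that the documents do not give. As an assumption only, multiplying 4.90 by √(1 − r²) for a correlation r between baseline and Month 12 of 0.3, 0.5 or 0.6 gives about 4.67, 4.24 or 3.92 at 105 per group. No single planning figure can therefore stand in for the ANCOVA decision.

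**The case against.** The strongest reply concedes the arithmetic and disputes its weight. The figure is a parenthesis in a sample size paragraph, placed straight after the 105 per group and SD 18 assumptions. It can be read as the smallest significant difference under those assumptions and not as a rule for the analysis. Protocol 10.4.2 and SAP 2.3.4 govern the test and ignore it. On that reading it is a 0.2 mL/min/1.73m² slip that changes nothing. Much of this stands: an analyst would very probably follow the ANCOVA, and no design quantity depends on 5.1. But the words express a decision, three sections repeat them, and no section makes them subordinate to the test.

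The larger figures at 165 per group also owe little to the slip itself. A correct 4.9 applied there would have alpha of about 1.4% and power of about 85.5%, against 1.05% and 83.1% for 5.1. That is right. Those figures mainly show what any fixed planning cut-off does at a larger n, which is a reason to prefer deletion to correction.

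The parenthesis also names one direction only, so its error rate is better put as about 2.1% against 2.5% in favour of everolimus. The 4.1% assumes a symmetric rule. The relative size of the discrepancy is the same.

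Finally, the protocol's Appendix 1 requires a written, approved amendment for any protocol change, so editing Protocol 10.7 costs more than editing the SAP. This affects how the correction is made, not whether it is needed.

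**Conclusion.** The threshold is wrong as written. From the plan's own inputs it is 4.90 (4.87 with the normal quantile), not 5.1, and the sentence disagrees with the specified two-sided 5% ANCOVA. The effect attributable to the slip is small: at 105 per group, two-sided alpha of about 4.1% instead of 5% and power of 77.8% instead of 80.1% at a true difference of 7.0. It is on the strict side, so the type I error is not inflated. The 105 and 165 per group are unaffected. Even at 165 analysed per group, a 5.1 cut-off would keep power above 80% at the planned effect, though well below that of the 5% test.

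The 4.90 holds for an unadjusted t-test with SD exactly 18 and 105 per group. The cut-off in the actual ANCOVA will depend on the residual SD and the number analysed. The sentence should be corrected because it bears on the primary decision, not because the design is at risk.

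**What to change.** Delete the parenthesis in Protocol 10.7 and in SAP 1.1 and 3, and state that the confirmatory decision rests only on the two-sided 5% ANCOVA test of Protocol 10.4.2 and SAP 2.3.4. If a figure is kept, give it as about 4.9 at 105 per group with an unadjusted SD of 18, and mark it as illustrative and not as a decision rule.

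The cost is wording only: sample size, test, alpha and conduct stay the same. The protocol edit can be included in an amendment. If the documents are already final, a note to file is enough; one is already attached to this SAP on another matter.

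A separate minor wording point, on which nothing above depends: Protocol Section 5 has "330 evaluable patients (165 in each treatment group) will be recruited", whereas Protocol 10.7 makes 165 per group the number randomised. Section 5 should say randomised.

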## 4 Change to protocol specified analyses

The study protocol was amended 5 times, the original protocol and all amendments are provided in [Appendix 16.1.1](#). Previous sections of this report describe the study conduct as amended. The key features of each amendment are given below:

**Amendment 1** (20-Jan2012), before generation of CRF and inclusion of first, introduced the following changes:

- Assessment schedule: Laboratory and GFR were shifted from Screening visit to baseline visit
- Additional assessment in Screening visit: Menopausal status and in all women of childbearing potential a pregnancy test

**Amendment 2** (26-Sep-2012), 15 patient had been randomized to the study. The major changes that were made to the protocol were as follows:

- Measurement of the Tacrolimus C-0h levels can now be performed as per local practice.
- Inclusion criteria – randomization 2 was rephrased for a clearer understanding.

- Inclusion criteria – randomization 3: AST and ALT levels were raised to  $\leq 5$  times ULN, evaluation of gamma GT was deleted due to the fact that it does not reflect a prognostically important mark.
- For a better understanding, exclusion criteria – randomization 2 was separated in 4 independent criteria. Platelet, neutrophil and white blood cell count was reduced to 50,000/mm^3, 1,000/mm^3 and 2,000/mm^3 respectively
- Former inclusion criteria – randomization 2 (now 6): Calculation mistake of concentration of hypertriglyceridemia was corrected.
- Graft loss was added as reason for premature patient withdrawal.
- Dispensing of study drug and instruction for use of study drug are described in more detail to avoid misuse.
- According to the adaptation of in- and exclusion criteria, the permission of study drug adjustment and interruption in case of inability of tolerance of the protocol-specific dosing scheme is described in more detail.
- PCP prophylaxis and treatment of oral candida will be performed according to local practice.
- It was added, that pregnancy outcomes must be collected for the female partners of any males who took study drug in this study

These amendments were not considered to have affected the interpretation of study results as they were minor.

**Amendment 3** (14-JUN2013): 57 patients had been randomized to the study:

Five sub-studies which will be conducted in selected centers were added to the protocol. In addition some editorial changes were performed.

**Amendment 4 (19-NOV-2014):** 186 patients had been randomized to the study:

The protocol had been refined to clarify the mandatory usage of corticosteroids in this study. Additionally, Inclusion Criterion 3/Exclusion Criterion 11 had been adjusted to include total abstinence as acceptable contraception method.

**Amendment 5 (19-AUG-2015):** 259 patients had been randomized to the study:

The purpose of this amendment was to adapt one exclusion criteria (Excl.Crit.N°5) to better align with given clinical praxis and patients' condition post liver transplantation. Therefore Exclusion Criterion 5 (at randomization) had been adjusted to allow inclusion of patients with hemoglobin < 6.0 g/dL (transfusion of erythrocytes concentrate during or after transplantation are allowed according to investigator discretion).

**Changes in statistical methods in comparison to the protocol:**

The Virus (HCV, CMV) and Hepatocellular Carcinoma (HCC) related secondary objective “• To evaluate rates of progression of HCV related allograft fibrosis are deleted. Reason is, that the in case from HCV the biopsies were not performed adequately.

The incidence of proteinuria of  $0.5 - <1.0$  g/day,  $1.0 - <3.0$  g/day and  $\geq 3.0$  g/day could not be analysed, because in urine analysis protein is measured in g/l and not in g/day. Therefore, proteinuria could be only documented as adverse event. Therefore proteinuria is defined as further adverse event of special interest.

CNV viral infection were defined as further adverse event of special interest.

Treatment emergent events were defined as all adverse started at baseline or later.

## 5 Appendix

### 5.1 Imputation rules

#### 5.1.1 Study drug

According to Novartis-Germany guidelines missing values in dates will be imputed by a simple way:

Missind day → replacement by 15

Missing month → replacement by 7

Everolimus and Tacrolimus are study medication. After treatment discontinuation this treatment are documented as "Immunosuppressive Medications". For the analysis of Everolimus and Tacrolimus this treatment have to be shifted from "Immunosuppressive Medications" to Study medication. If WHO-DD-preferred-name are EVEROLIMUS or TACROLIMUS, TACROLIMUS MONOHYDRATE in "Immunosuppressive Medications", the record will be shifted to "Study medication". If the end-date of the medication is later than the last visit (e.g. Month 12) or the medication is "continuing after study", the end-date will be set to date of last visit. This adaption is necessary to calculate the treatment duration and the mean dose over the study for everolimus and tacrolimus.

Duration of exposure will be calculated until end of study. That means, that the period after end of treatment will also be included.

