## **10.3 Treatments (study drug, rescue medication, other concomitant therapies, compliance)**

### **10.3.1 Study medication**

Duration (days) of drug exposure to each individual component of the immunosuppressive treatment regimen will be summarized using descriptive statistics. Duration of drug exposure will be calculated as the difference between the last and first day of drug application +1. Dosage averages will be calculated including and excluding zero doses for periods of temporary interruption of treatment regardless of whether this was due to safety reasons or patients' non-compliance. Daily dose levels will be summarized descriptively. Frequencies of the number of patients with any dose reduction (including temporary dose interruption) as well as the number of dose reductions by reason will be given. These analyses will be performed by treatment group for the safety set.

Frequency tables displaying cumulative frequencies of 'crude rates' will be presented for the number of patients with trough levels below/within/above the defined therapeutic windows drug and by visit. If appropriate, treatment groups will be compared exploratory using the Pearson's Chi-Square test (where all expected numbers are at least 1), otherwise Fisher's exact test will be used ([Campbell 2007](#)). Furthermore, frequency tables for the number of

patients with trough levels below/within/above the defined therapeutic windows drug and by period.

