### **2.1.1 General definitions**

Study treatment:

- EVR/TAC
- TAC

Date of randomization: Date of Visit 2 (Baseline)

Date of first treatment: max (date of randomization, min (start date of dosage administration\*))

Date of last treatment: Max (max(end date of dosage administration\*), Last known date subject took study treatment~)

\*: documented on Dosage Administration Record form

~: documented on End of Treatment form

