## **2.3 Treatments (study treatment, rescue medication, concomitant therapies, compliance)**

### **2.3.1 Study treatment / compliance**

Duration (days) of drug exposure to each individual component of the immunosuppressive treatment regimen was summarized using descriptive statistics. Duration of drug exposure was calculated as the difference between the last and first day of drug application +1. Dosage averages were calculated including and excluding zero doses for periods of temporary interruption of treatment regardless of whether this was due to safety reasons or patients' non-compliance. Daily dose levels were summarized descriptively. Frequencies of the number of patients with any dose reduction (including temporary dose interruption) as well as the number of dose reductions by reason were given. These analyses were performed by treatment group for the safety set.

Frequency tables displaying cumulative frequencies of 'crude rates' will be presented for the number of patients with trough levels below/within/above the defined therapeutic windows drug and by visit.

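### SAP 5.1.1 runs everolimus and tacrolimus exposure to end of study without reconciling it with SAP 2.1.1, SAP 2.3.1 or protocol 10.3.1, so the exposure tables can overstate time on the randomised regimen

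*SAP*

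**What the plan says.** Four places bear on how long a patient counts as exposed.

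- **Protocol 10.3.1**: "Duration of drug exposure will be calculated as the difference between the last and first day of drug application +1". The summary is made for each component of the regimen, by arm, in the safety set.
- **SAP 2.3.1** keeps that rule, in the past tense: "Duration of drug exposure was calculated as the difference between the last and first day of drug application +1".
- **SAP 2.1.1** defines a date of last treatment. It is the later of the latest end date on the Dosage Administration Record and an entry on the End of Treatment form, "Last known date subject took study treatment".
- **SAP 5.1.1** deals with everolimus and tacrolimus that are recorded as general immunosuppressive medication after discontinuation. These records are moved into study medication. If they run past the last visit or are ongoing, "the end-date will be set to date of last visit". The reason given is "This adaption is necessary to calculate the treatment duration and the mean dose over the study for everolimus and tacrolimus". The section then adds "Duration of exposure will be calculated until end of study" and "That means, that the period after end of treatment will also be included".

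Two further provisions matter. SAP 5.1.3 removes tacrolimus and everolimus from the analysis of other immunosuppressive medication. The list of changed statistical methods in SAP Section 4 does not mention the exposure rule.

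**The concern.** Stopping study drug does not end participation. Protocol 5.2 says that such patients are not to be considered withdrawn, and protocol 6.6.3 and 6.6.8 require the Month 12 assessment for everyone randomised. End of treatment and end of study can therefore be months apart, and an exposure rule that stops at one gives a different answer from a rule that stops at the other.

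The exposure and mean-dose tables are where a reader looks to see how long, and at what dose, each arm received its assigned regimen. Under SAP 5.1.1, tacrolimus taken after an Arm I patient has stopped everolimus enters that arm's study-drug duration and mean dose. Protocol 10.4.2 foresees control patients switching to the investigational regimen. If such a patient's everolimus is recorded after discontinuation, it would appear as study-drug exposure in the control column. Because SAP 5.1.3 takes both drugs out of the other immunosuppressant analysis, no planned table separates use before end of treatment from use after it.

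**Working it through.** The documents state no exposure figure, so there is none to reproduce. The check compares the rules on the same patients and then sizes the gap under stated assumptions.

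**Inputs.** Month 12 is day 360 (protocol Table 4-1 and assessment schedule). Duration is last day minus first day plus 1 (SAP 2.3.1, protocol 10.3.1). The stopping days and stopping proportions below are assumptions, because neither document gives the rate or timing of treatment discontinuation.

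**Single patients.** Each has the first dose on day 1 and stops randomised treatment on day 90.

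| Patient after day 90 | To the SAP 2.1.1 date | SAP 5.1.1, milder reading | SAP 5.1.1, literal |
|---|---|---|---|
| Attends Month 12, takes neither drug | 90 − 1 + 1 = 90 | 90 | 360 − 1 + 1 = 360 |
| Attends Month 12, tacrolimus recorded throughout: tacrolimus | 90 | 360 | 360 |
| Same patient: everolimus, not retaken | 90 | 90 | 360 |
| Leaves the study on day 90 | 90 | 90 | 90 |

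The milder reading takes last drug application to mean the last recorded intake of that drug from any source, capped at the last visit. The literal reading follows the closing two sentences of SAP 5.1.1 as they stand. Where the readings part from the SAP 2.1.1 date, the excess for this patient is 360 − 90 = 270 days. The rules agree for a patient treated to Month 12 and for one who leaves the study on stopping.

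**Group mean.** Let a proportion p stop on day t and stay in follow-up, with all others treated to day 360.

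- Mean time on randomised treatment = (1 − p) × 360 + p × t.
- With p = 0.20 and t = 180: 0.8 × 360 + 0.2 × 180 = 288 + 36 = 324 days.
- If every stopper is counted to day 360, the mean is 360 days, and 360 / 324 = 1.111, or +11.1%.
- If only half of the stoppers are counted to day 360: 288 + 0.2 × (0.5 × 360 + 0.5 × 180) = 288 + 54 = 342 days, and 342 / 324 = 1.056, or +5.6%.

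**Range over the assumptions** (p from 10% to 30%, t from day 60 to day 270).

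- Lowest: 0.9 × 360 + 0.1 × 270 = 351, and 360 / 351 = 1.026, or +2.6%.
- Highest: 0.7 × 360 + 0.3 × 60 = 270, and 360 / 270 = 1.333, or +33.3%.
- With only half of the stoppers counted to day 360, the range is +1.3% to +16.7%.

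The effect on mean dose has no fixed direction. It depends on the doses recorded after discontinuation and on whether days without drug enter the average.

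**The case against.** The best defence is that SAP 5.1.1 applies SAP 2.3.1 rather than contradicting it. Section 2.3.1 speaks of each drug component and of drug application. It does not mention randomised treatment and does not cite the date in 2.1.1. Section 5.1.1 moves only records of actual everolimus or tacrolimus use, caps them at the last visit and gives its reason. On that view, end of study is simply the window for counting intake, and a patient who never retakes a drug has no later record to move. Exposure to end of study also fits the adverse event window, since SAP 2.6.1 treats every event from baseline onwards as treatment-emergent.

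Much of this stands. The milder reading is available, and under it recorded intake is not overstated. It does not remove the difference from the date in SAP 2.1.1, and the closing sentence of 5.1.1 goes further than that reading needs. It also leaves on-regimen and off-regimen use in one figure.

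Several stronger inferences are tempting, and the documents do not support them:

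- **That every patient who discontinues is affected.** Patients who leave the study on stopping are not, and on the milder reading neither are those with no later record.
- **That the 20% drop-out in the sample size gives the size of the error.** It is a planning allowance for drop-out, not a rate of stopping treatment while remaining in follow-up. SAP 2.3.6 says only that study discontinuations were below 20%.
- **That differential discontinuation would be hidden.** SAP 2.2.1 reports treatment and study discontinuation with reasons by arm. SAP 2.6.1 tabulates adverse events leading to discontinuation. SAP 2.3.1 and 2.7 compare trough levels with the target windows by visit.
- **That adverse event rates would be distorted.** SAP 2.6.1 plans numbers and percentages of patients, with no exposure-adjusted rate.

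**Conclusion.** The point holds as an unreconciled and undeclared difference in definition. As written, SAP 5.1.1 gives a longer exposure than the SAP 2.1.1 date of last treatment for patients who stop randomised treatment and stay in follow-up. This covers all such patients on the literal wording, and only those with later everolimus or tacrolimus records on the milder reading. In both cases the by-arm tables overstate time on the randomised regimen.

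The size cannot be established from the documents. The +11% rests on three assumptions: 20% stop, they stop at day 180, and all are counted to day 360. It falls if some leave the study or take no further drug. The consequence is confined to descriptive exposure and dose tables. The primary ANCOVA does not use exposure, and the crude adverse event percentages and disposition tables do not change.

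**What to change.** 1. Reconcile SAP 5.1.1 with 2.1.1 and 2.3.1, so that one rule defines the end of exposure.
2. Make the main table duration and mean dose from first treatment to the date of last randomised treatment.
3. Show everolimus and tacrolimus use from any source to end of study in a separate, clearly labelled table, counting only days with recorded intake. This keeps the purpose that SAP 5.1.1 gives for moving the records.
4. List the change in SAP Section 4.

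The cost is revised SAP wording and one extra table. The headline exposure will be shorter than under SAP 5.1.1. No new data are needed, because the dosage, end-of-treatment and immunosuppressant records are already collected.
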